2.7 PEP Study Pilot

In order to test the feasibility of patient recruitment and study implementation, a pilot study was conducted (IRB 91478, The PEP Study: Precision Exercise Prescription among lung cancer patients, approved 7/3/2016).

Between 7/7/2016 and 10/11/2016, n=18 lung cancer patients were recruited into the intervention program at their pre-surgery consult with [name]. Every eligible patient was approached, and all patients approached (100%) agreed to participate in the intervention. Their physical function was assessed with 6MW test, SPPB, and AM-PAC score. The testing and precise exercise prescription was implemented within normal clinic workflow and clinic space by a trained physical therapist ([name]) using existing space in the clinic of Thoracic Surgery. The intervention included individually-prescribed exercise modes (mobility, flexibility, callisthenic, aerobic, and resistance) and dosages (low, moderate, high) tailored to the patient's AM-PAC mobility stage.

The baseline observed 6MW distance varied from 209-679m with a mean distance of 467 ± 119 m. Normal 6MW distance for healthy 60-69 year olds is 572m for men and 538m for women. For ten patients, post-operative 6MW distances were obtained prior to 10/15 (max. follow-up time 20 post-operative days within the pilot). Compared to comparable control patients (for whom 6MW distances at comparable pre- and post-time points were available) PEP patients maintained their physical function and experienced a lesser reduction in 6MW distance (median 6.8% decline in PEP and 18.7% in controls, see Figure 1). Although this comparison is not based on a randomized study, it is notable that the decrease (47m) in 6MW distance in the controls exceeded the minimal clinically important distance, despite the time points achieved at this point being very early in the intervention process. To date, only one patient has dropped out (5.5% drop-out rate).

A follow-up phone evaluation of the PEP intervention showed that patients planned to exercise an average of 4.7 days per week and 93% agreed (86% strongly) that exercise should be part of their cancer treatment; 86% also strongly agreed with the statement that they believe that the exercise program will have a positive effect on their cancer treatment. Several patients noted that they loved being in the program and the effort of our team. They emphasized that the exercise intervention helped them immensely with recovery from surgery.

In conclusion, these preliminary results demonstrate that: (1) our team has successfully worked together on the PEP study intervention, generated pilot data, and two scientific abstracts;^{90,91} (2) lung cancer patients differ dramatically in their functional status, independent of age, sex, and stage, requiring individualized interventions; (3) the PEP intervention was feasible within the existing workflow of a high-volume surgical clinic, with only the addition of a physical therapist to manage the intervention; (4) the PEP intervention is welcomed by patients and appears to show early efficacy; and (5) our assumptions for anticipated patient recruitment (65%) and drop-out rates (15%) are conservative. Overall, this pilot work sets the base for a successful clinical trial.

3 STUDY DESIGN

3.1 Description

This is a Phase 3 study aimed at investigating the effects of a personalized exercise program (PEP) in NSCLC patients (stage I, II, IIIa) and secondary lung cancer patients undergoing surgical treatment at the University of Utah and comparing the intervention to the current standard of care (no exercise program).

Eligible patients will be randomized between two arms (1:1 ratio) prior to the surgery and will be followed for approximately 6 months post-surgery:

- An Intervention Arm (referred to in materials as Group 1), which features pre- and post-surgery PEP interventions.
- A Control Arm (referred to in materials as Group 2), which does not include a personalized exercise program (the standard of care). Patients randomized to Group

2 will be given the opportunity to participate in a PEP-intervention session providing exercise counseling after the 6 month assessment and will receive a free activity tracker for their participation.

3.2 Number of Patients

The target enrollment for the randomized clinical trial is 200 patients (approximately 106 men and 94 women). It is estimated that 300 patients will be approached about the study, which will achieve a conservative recruitment rate of 65%.

3.3 Number of Study Centers

This study will open at a single center at the Huntsman Cancer Institute. Study procedures may be performed at the Huntsman Cancer Hospital, the University of Utah Farmington clinic, or remotely. The remote option will only be used in circumstances when staff is not able to perform study procedures on site. Staff will take necessary steps to ensure participant safety and confidentiality at all times when performing procedures remotely.

3.4 Duration

Participants will be recruited over the course of 33 plus duration of COVID-19 adjustments months. The estimated total duration of the study from the first enrollment to the end of the last 6-months follow-up is 4 years plus duration of COVID-19 adjustments.

4 ELIGIBILITY CRITERIA

This eligibility checklist is used to determine patient eligibility and filed with investigator's signature in the patient research chart.

Patient No. _____ **Patient's Initials: (L, F, M)** _____

4.1 Inclusion Criteria

Yes/No (Response of "no" = patient ineligible)

- 4.1.1 _____ Male or female subject aged ≥ 18 years.
- 4.1.2 _____ Suspected (per the treating physician) diagnosis of primary lung cancer stage I, II, or IIIa OR secondary lung cancer.
- 4.1.3 _____ Disease amenable to surgical resection in the opinion of the treating surgeon.
- 4.1.4 _____ Patients must be able to follow directions and complete questionnaires and exercise diaries in English.
- 4.1.5 _____ Patients must agree to be randomly assigned to either Intervention or Control Group.

4.2 Exclusion Criteria

Yes/No (Response of "yes" = patient ineligible)

- 4.2.1 _____ Deemed ineligible for surgery by the enrolling physician
- 4.2.2 _____ Abnormalities on screening physical exam judged by study physicians or supervising physical therapist to contraindicate participation in exercise program compliance.
- 4.2.3 _____ Alcohol or drug abuse as judged by study physicians.
- 4.2.4 _____ Significant mental or emotional problems that would interfere with study participation, or as assessed by the NCCN Distress Thermometer. Any value higher than 7 on the NCCN Distress Thermometer will trigger further assessment, but ultimately enrollment into the clinical trial will be determined by the enrolling physician.

I certify that this patient meets all inclusion and exclusion criteria for enrollment onto this study.

Investigator Signature

Date

Time

5 INTERVENTION

5.1 Group 2 Delayed Intervention Group

Patients randomized to Group 2 will not experience any changes in the standard of care for lung cancer patients according to their cancer stage. Although patients are encouraged to increase walking both in the pre-surgery and post-surgery period, there is no formalized pre-surgery exercise program. Upon study completion (at the 6 month post-surgery follow-up visit), participants in Group 2 will be offered a PEP-intervention session with precision exercise counseling and receive a free activity tracker.

5.2 Group 1-Intervention Group

The PEP intervention involves a combination of home-based exercise as well as in-patient exercise. The exercise modes will include basic transfer and calisthenics mobility, aerobic, and resistance exercises and will be performed in various postures (supine, sitting, standing, and walking) with variable challenges (level walking, bending, inclines, steps, and squatting).

For patients randomized to Group 1, the PEP intervention will be personalized, implemented, and modified (based on the patients AM-PAC mobility stage) by a licensed physical therapist in face-to-face, virtual, or phone meetings (~30-40 minutes). An exercise education manual, specifically developed for this study, will be used by the physical therapist to educate the patients on all aspects of starting and maintaining the exercise intervention.

5.2.1 Inpatient Sessions

The post-surgery inpatient PEP intervention will be performed under the supervision of the physical therapist in accordance with the exercise education manual and the patient's AM-PAC mobility stage.

5.2.2 Home-Based Exercise

The outpatient exercises will be performed both pre- and post-surgery and will be done at home, the HCI Wellness Center, a recreational center, or similar locations.

The study physical therapist will go over (verbally and in writing) the individual exercise modes and dosages to be performed at home. The individual modes and dosages to be performed at home can also be discussed via phone and the physical therapist may email or send through MyChart the exercise instruction sheets. Although individually-prescribed, the exercise mode and dosage will be standardized with respect to the patient's AM-PAC mobility stage (as shown in Figure 2). For example, a patient in AM-PAC mobility stage 3 will progress from walking on level surfaces for 10 minutes per day at a "somewhat hard" perceived exertion with the ability to talk but not sing during walking. The rate of steps/minute will be ~100. Additionally, this patient will also perform squatting exercise at the same perceived exertion for short bouts that add up to 5 minutes

per day. These aerobic and resistance exercises will be progressed to 20 minutes and 10 minutes per day respectively as they progress to AM-PAC mobility stage 4.

Patients will be given access to instruction sheets demonstrating exercise modes along with exercise tools (e.g., light weights and external resistance bands), tracking diary/calendar, and activity tracker (see note below) for the home-based exercise program. These instruction sheets may be emailed, mailed, or sent through the participant's electronic medical record (MyChart).

Telephone calls or TeleHealth interactions between the participant and the study team will take place weekly to answer questions, optimize patient engagement, and adjust exercise prescriptions remotely as needed. These interactions will be based upon the Motivation and Problem Solving (MAPS) approach, which draws on key aspects of motivational interviewing (MI), cognitive-behavioral therapy, chronic care models, and case management/patient navigation. These weekly phone calls may either be delayed or unsuccessful dependent on the participant's schedule, availability, and whether or not they answer. However, study staff will make an effort to reach the participant if the participant continues to not answer or return the phone calls. In instances where a participant has felt burdened by these phone calls, research staff may perform the calls less frequently for these participants to maintain patient retention. Study staff may utilize text messaging and/or email in order to remind participants of future appointments/calls or to coordinate a day and time to reach the participant by phone. If study staff cannot get ahold of the participant, this will not be considered a deviation. Study staff may also text and/or email the participants to send reminders, schedule study procedures, etc.

Ongoing monitoring of attitudes and barriers to exercise will occur and strategies for encouraging uptake of the exercise intervention will be individually tailored. U of Utah TeleHealth capabilities, including video chat, will be used to augment telephone communications.

Note: the activity tracker, a consumer wearable device (e.g., Fitbit Zip Wireless Activity Tracker), will be used as a pragmatic motivational and self-monitoring tool to improve participant exercise efficacy and home exercise program adherence.⁸⁶

[figure not shown]

Figure 2: AM-PAC stages (according to Arbane) and corresponding exercise modes and dosages.

5.2.3 Interruption and Discontinuation

The PEP intervention is already personalized, implemented, and modified based on an individual's patient characteristics. However, if, at any time during the study a participant develops an illness that contraindicates exercise in the opinion of the enrolling physician (including but not limited to those described in exclusion criterion 4.2.1), the patient's primary care physician will be consulted regarding whether and when it would be safe to re-start the exercise program.

Should any participant develop any condition that would limit their ability to fully participate in the prescribed protocol, the participant would be temporarily, or if necessary permanently, withdrawn from the study.

Protocol name: Precision Exercise Prescription Randomized Clinical Trial
Version Date:24NOV2021
Previous Version: 16JUN2021
Principal Investigator: [name], PT

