8.6 During the Follow-Up (Outpatient)

For patients randomized to Group 1, weekly telephone calls or TeleHealth interactions between the participant and the study team will continue as described in section 8.2.

8.7 Follow-Up Clinic Visits (2 and 6 Months Post-Surgery).

These visits are directly aligned with the patient's clinic visits and is contingent on clinic and patient availability. During times of unforeseen external impact, the 2 month visit may occur up to 4 months post-discharge and the 6 month visit may be completed up to one year post-discharge depending on the health of the patient and surgical policies. This window may increase if patient and surgical policies require it. The 6 month questionnaire may be completed on the date of the visit up to one year after the visit. The following procedures will be completed at the follow-up visits scheduled approximately 2 and 6 months after surgery:

- Assessment by physical therapist including AM-PAC mobility score (outpatient form). Staff may administer the AM-PAC with the participant remotely if the form cannot be given in clinic.

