10.2 Outcomes, Power, and Sample Size Considerations

Objectives and endpoints are described in Section 1. Covariates used in sensitivity or mediation analysis of the objectives will be age, gender, baseline smoking status, primary or secondary lung cancer, neoadjuvant treatment, tumor stage, baseline level of outcome, pain, and sleep.

Power calculations are based on the group effect in an analysis of covariance for the 6MW test at 8 weeks, with baseline 6MW test as covariate. The planned sample size ($n = 200$) allows for a 25% drop out rate (the main reasons for drop outs observed during the pilot study was found to be complications or poor health status preventing follow-up visits as well as distance to study site), leaving at least 150 subjects evaluable for the primary endpoint. The hypothesis is that the difference in the 6MW distance between the study arms (Intervention vs. Control) will be ≥ 39.95 m. This effect size stems from a meta-analysis where 4 weeks of post-surgery exercise training provided a 39.95 increase in the 6MW distance in NSCLC patients.⁸⁷ Consistent with Arbane,¹¹ $SD = 100$ m and correlation = 0.5 between repeated 6MW test measurements on the same subject are assumed. Power to detect the treatment effect was estimated by simulation (in R) of an analysis of covariance model with 6MW test at 2 months postsurgery as outcome, treatment group as primary predictor and pretreatment 6MW test as covariate. Pre and post 6MW test was assumed to be bivariate normally distributed.

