10.3 Primary Endpoint Analysis

Analyses will include all patients that are evaluable for our primary endpoint (expected at least $n=150$). The primary outcome will be the group effect for an analysis of covariance model with 6MW test at 2 months post-surgery as outcome and pretreatment 6MW test as covariate, tested at the nominal two-sided 0.05 significance level. A sensitivity analysis will be performed with additional adjustment variables (listed as covariates in Section 10.1). Missing data will be handled using multivariate imputation by chained equations⁸⁸ as implemented in the R package “mice”.

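### Section 5.2.3 withdraws patients from the study, not only from the exercise programme, and no provision keeps their outcome assessments; the loss probably falls mainly on Group 1

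*Combined protocol and SAP*

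**What the plan says.** Section 5.2.3 has two paragraphs with different consequences. For an illness that contraindicates exercise, the question put to the primary care physician is "whether and when it would be safe to re-start the exercise program"; this pauses the exercise only. The next paragraph is wider: "Should any participant develop any condition that would limit their ability to fully participate in the prescribed protocol", the consequence is that "the participant would be temporarily, or if necessary permanently, withdrawn from the study".

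The rule is placed under Section 5.2, which describes Group 1. Section 5.1 says of the other arm: "Patients randomized to Group 2 will not experience any changes in the standard of care". Section 8.6 gives the regular contact to one arm: "For patients randomized to Group 1, weekly telephone calls or TeleHealth interactions between the participant and the study team will continue". The Section 6 schedule marks the exercise and call items as applying only to patients in the programme; the 6MW, SPPB and questionnaires carry no such mark. Section 14.4 lists adjusting, temporarily interrupting and permanently discontinuing the intervention as actions after an adverse event, without saying that the patient leaves the study.

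On analysis, Section 10.3 says "Analyses will include all patients that are evaluable for our primary endpoint" and also "Missing data will be handled using multivariate imputation by chained equations". It does not say whether withdrawn patients are imputed or which variables enter the model. Section 10.2 gives the pilot drop-out reasons as "complications or poor health status preventing follow-up visits" together with distance to the site.

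**The concern.** Stopping an intervention and leaving a study are different events. A patient who can no longer exercise can still attend the 2-month visit and, where safe, walk for six minutes. Section 5.2.3 as worded lets the first event end the second.

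The trigger is a condition that limits participation, and the primary outcome is walking distance, so the patients removed are likely to be those who would walk least. If this happens more often in Group 1, its observed mean rises for a reason unrelated to benefit. Outcomes not measured at 2 months cannot be recovered later. The only sensitivity analysis planned for the primary endpoint adds covariates; the missing-data sensitivity analyses in Section 10.4 concern indirect effects only.

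**Working it through.** **Inputs from the documents.** 200 randomised 1:1; 25% drop-out; SD 100 m; correlation 0.5 between repeated 6MW tests; target difference 39.95 m; two-sided 0.05; ANCOVA on baseline 6MW (Sections 3.1, 3.2, 10.2, 10.3).

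**The plan's own figure.** 200 × (1 − 0.25) = 150 evaluable, as stated. The text gives no power for the primary endpoint, so I computed it. Residual SD = 100 × √(1 − 0.5²) = 86.6 m. At 75 per arm, SE = 86.6 × √(2/75) = 14.14 m, and 39.95/14.14 − 1.96 = 0.865, which gives 80.6% (80.1% with the t distribution).

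**Assumptions the documents do not supply.** The share of Group 1 withdrawn as the sickest: 5%, 10% or 15%. The correlation ρ between sickness and the 2-month 6MW: 0.5 to 1.0. All other loss is random, up to 25% per arm. There is no true effect.

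**Closed-form bias.** Removing the lowest fraction p of one arm on the sickness score raises that arm's mean score by φ(z_p)/(1 − p) standard deviations. The mean 2-month 6MW then rises by 100 × ρ × that amount. Baseline adjustment takes back 0.5² of it. So

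bias ≈ 100 × (1 − 0.25) × ρ × φ(z_p)/(1 − p).

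- p = 5%: 75 × ρ × 0.1031/0.95 = 8.1ρ, or 4.1 to 8.1 m
- p = 10%: 75 × ρ × 0.1755/0.90 = 14.6ρ, or 7.3 to 14.6 m
- p = 15%: 75 × ρ × 0.2332/0.85 = 20.6ρ, or 10.3 to 20.6 m

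**Simulation of the planned ANCOVA** (1,500 runs per setting, complete cases; the first range in each row runs from ρ = 0.5 to ρ = 1.0):

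| Withdrawn as sickest, Group 1 / Group 2 | Bias toward the programme | False-positive rate |
|---|---|---|
| 0% / 0% | 0.6 m (noise) | 5.3% |
| 5% / 0% | 4.4 to 7.8 m | 7 to 9% |
| 10% / 0% | 6.8 to 14.4 m | 9 to 19% |
| 15% / 0% | 9.7 to 21.0 m | 11 to 37% |
| 10% / 10% | about 0 | 5 to 8% |
| 10% / 5% | 3.0 to 7.4 m | 6 to 11% |
| 5% / 10% | −2.5 to −6.6 m | 6 to 10% |

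The two methods agree. As a share of the target, 4/39.95 is 10% and 21/39.95 is 53%.

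**Does imputation repair it?** With a model holding only arm and baseline 6MW, hardly at all: 14.3 m instead of 14.4 m (10% / 0%, ρ = 1). A further check assumed 30% loss in Group 1 and 20% in Group 2, a true effect of about 40 m, and a discharge 6MW measured before withdrawal. If loss depended on function at discharge, adding the discharge 6MW to the model returned about 40 m. If it depended on the 2-month function itself, the bias fell by only about a tenth to a half.

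**The case against.** The strongest reply is that 5.2.3 is loosely worded and will do little harm.

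- **Both arms are covered.** The text refers to any participant and to the protocol, not to exercise. This stands: the concentration in Group 1 is inferred from where the rule sits, from Group 2 having no programme to fall short of, and from the weekly calls. In both arms the follow-up 6MW is omitted when judged unsafe (Sections 8.5 and 8.7), so a Group 2 patient with the same condition is not sure to be measured either.
- **Withdrawal may be temporary, and poor function need not trigger it.** The programme is tailored to mobility stage and can be adjusted. A patient who returns may still reach the 2-month test, and Section 8.7 allows wider windows in some circumstances. Complications, length of stay and readmission can come from medical records (Section 9.3). This also stands, so total loss of data is not established.
- **Imputation is planned.** A reader might infer from the evaluable-patient wording that withdrawn patients are simply not analysed, or that no analysis could repair the loss. The first is one of two readings of Section 10.3, and the second holds only under some mechanisms. The discharge 6MW is scheduled, and Section 9.3 plans prediction of missing 6MW values. But the imputation variables are not stated, and the discharge visit falls 1 to 8 weeks after discharge, so some patients could be withdrawn before it.
- **Power.** A reader might also infer a loss of power. With 30% and 20% lost from 100 per arm, 70 + 80 = 150 remain. SE = 86.6 × √(1/70 + 1/80) = 14.17 m, and power is 80.5% against 80.6%. The issue is bias, not power.

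None of this supplies the missing statement that assessments continue after a patient stops the programme.

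**Conclusion.** The concern holds as a gap in the protocol with a probable, not certain, direction. As written, 5.2.3 permits outcome collection to end because of a health condition arising after randomisation, and no other section offsets it.

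The bias favours the programme only if withdrawal is more frequent in Group 1 and the withdrawn patients walk less. On the assumed 5-15% withdrawn from Group 1 alone, it is about 4-21 m, roughly 10-50% of the 39.95 m target, with false-positive rates of 7-37%. It is about zero with equal withdrawal and changes sign if Group 2 loses more. These figures illustrate sensitivity and do not forecast, because the documents give no withdrawal rate.

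A reader might go further and conclude that the trial is certain to overstate the effect, for example by 15-23%, as one gets by assuming 30% against 20% loss and a deficit of 65-102 m in those lost. The documents supply neither the split nor the deficit, so that size cannot be attributed to the plan.

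**What to change.** Leave every clinical decision on pausing, adjusting or stopping exercise as it is. Then:

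1. Reconcile the two paragraphs of 5.2.3 with the Section 6 schedule and the Section 14.4 list of actions, so that interrupting or stopping the programme is distinct from leaving the study. Simply replacing study withdrawal with withdrawal from the programme is not advisable: it would make every limiting condition a trigger for stopping exercise, although Section 14.4 also allows adjustment. That would be a new clinical rule.
2. State that the scheduled 6MW (where safe), SPPB, questionnaires and record abstraction continue in both arms unless the patient withdraws consent.
3. In Section 10.3, analyse all randomised patients by assigned arm, say that withdrawn patients are included in the imputation, and name its variables, including the discharge 6MW. A sensitivity analysis under missing-not-at-random assumptions would show how much depends on the remaining gaps.
4. Report withdrawals, with reasons and timing, by arm.

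The cost is a short amendment and some extra follow-up effort for patients who stop the programme, at visits already aligned with clinic visits. Patients for whom the 6MW is unsafe will still be missing, so the change reduces the problem without removing it.
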